### **16.2 Missing, unused & spurious data**

We will ensure that missing data is kept to a minimum. Results of all index and reference tests will be recorded. We will investigate patterns of missingness in the development and validation cohorts because if a predictor is difficult to obtain in practice, then the model including it may not be of clinical relevance. In the event of missing data, multiple imputation will be used to impute missing values in order to avoid bias and make best use of the data, by replacing missing values with plausible values based on the distribution of the observed data.

Full detail will be provided in the Statistical Analysis Plan (SAP).

### **16.3 Procedures for reporting deviation(s) from the original SAP**

These will be submitted as substantial amendments where applicable and recorded in subsequent versions of the protocol and SAP.

### **16.4 Termination of the Study**

Progression criteria for the internal pilot phase is described in section 13. There is potential for the study to terminate early if our funder assesses the study as not being feasible following an assessment of progress against our targets at the end of the internal pilot with input from our SSC.

### **16.5 Inclusion in analysis**

All participants with reference test data will be included in the analysis.

## **17 Analysis**

### **17.1 Diagnostic prediction model**

We have chosen to use three separate logistic regression models to develop numerical tools that will predict the urodynamic causes of LUTs using variables gathered by simple community-based tests. An alternative approach would be to use multinomial regression to investigate factors influencing the three diagnoses simultaneously, but such models require larger sample sizes to estimate the multiple parameters required [13]. For example, 11 predictors and three conditions would require 24 parameters which is not feasible in terms of cost and recruitment period. We will investigate patterns of missingness in the development and validation cohorts because if a predictor is difficult to obtain in practice, then the model including it may not be of clinical relevance. In the event of missing data, multiple imputation by chained equations (MICE)[14] will be used to impute missing values in order to avoid bias and make best use of the data, by replacing missing values with plausible values based on the distribution of the observed data. 10 imputed datasets will be created separately for each cohort.

#### **17.1.1 Model development**

Candidate predictor variables will be selected from those listed in the Table above. Their selection has been informed by subject knowledge using literature review and expert judgement. As predictor distributions should be wide to facilitate reliable predictions, we will explore the distribution of each predictor prior to selection. Relationships between predictors will also be investigated; where indicated we will group related variables into a composite variable or exclude if highly correlated with other variables. Candidate predictors will not be selected based on univariable analyses; this practice is discouraged because predictors that may be important in a multivariable model can be missed and may also lead to overoptimistic models. Therefore, all selected candidate predictor variables will be included in the multivariable logistic regression models without evaluations of association between outcome and predictor and assessment of statistical significance. To gain maximum diagnostic information, continuous variables will not be categorised. The linearity of continuous variables will be tested with restricted cubic splines. This may lead to the inclusion of non-linear terms in the models thus increasing the number of variables in the models. Overfitting, optimism, and miscalibration of the models will be addressed during model development by applying shrinkage using the least absolute shrinkage and selection operator (LASSO) method [15]. We chose this method because some regression coefficients may be shrunk to zero. Advantages of using shrinkage as part of our selection criteria of predictors include being able to drop variables with a coefficient of zero, and preventing

very extreme predictions. This allows models to be made as parsimonious as possible improving performance for a validation cohort.

### **17.1.2 Model validation and estimation of diagnostic accuracy**

The predictive performance of each model will be assessed in terms of discrimination, that is the ability to distinguish between those who do or do not have a particular diagnosis, and calibration meaning agreement between predicted and observed probabilities. Discriminative ability will be assessed using the c-index. For a logistic model, this is equivalent to the area under the ROC curve (AUC). Bootstrap resampling will be used to calculate 95% confidence intervals for the c-statistic. From the qualitative research we will ascertain distributions of probability (risk) thresholds for clinical usefulness of the prediction in guiding treatment of each condition. The sensitivity and specificity for these risk thresholds will be plotted on an ROC plot for each model and confidence intervals computed. Calibration will be evaluated in two ways. Within each quintile or decile of predicted probability (depending on the distribution of data), the average predicted probability will be compared with the corresponding observed proportions. Calibration plots of average observed probability against predicted probability will be used to visually assess calibration. We will also quantify calibration by estimating the calibration slope of the prognostic index (linear predictor) using logistic regression with the linear predictor as the covariate. The value for the calibration slope should ideally be one signifying perfect agreement between the predicted probabilities and the observed probabilities. A calibration slope  $< 1$  indicates that a model over-predicts while a calibration slope  $> 1$  indicates under prediction.

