### 3.2 Study Schema

## 4 Background

The syndrome of lower urinary tract symptoms (LUTS) occurs mostly in older men and is a bothersome condition detrimental to quality of life (QoL). It can usually be managed without invasive treatment and is very rarely a threat to life or long term health. Male LUTS accounts for four presentations each month in an average sized GP practice (CPRD, 2014). This rate of presentation makes it difficult for GPs to gain sufficient expertise to be confident about diagnosis and management. Consequently, men are frequently referred to urology specialists who often recommend treatments that could have been initiated in primary care. Clinical uncertainty also leads to variation in referral patterns between individual GPs, practices and localities. To address this, the National Institute for Health and Care Excellence (NICE) issued guidance for Male LUTS in 2010 (revised 2015) mapping out initial assessment and conservative management within primary care [1]. Despite this the proportion of men referred to urology services following an incident presentation of LUTS rose from 10% in 2009 to 30% in 2013 (CPRD 2014) at an approximate extra cost to NHS England of £2 million. Implementation projects commissioned by the NHS concluded that further support with access to simple accurate tests, diagnostic protocols and decision aids was needed to facilitate patient management in primary care and ensure best value for patients and the NHS from specialist referral [2].

One of the difficulties faced in primary care is obtaining and interpreting simple clinical measurements that differentiate causes of male LUTS and hence guide effective symptom management. The underlying conditions that disturb lower urinary tract function, with their approximate prevalence are: detrusor overactivity (57%), bladder outlet obstruction (31%), and detrusor underactivity (16%). The diagnoses may appear individually or in combination. An additional contribution to male LUTS arises from ageing-related changes in fluid homeostasis which commonly result in nocturnal polyuria (30%) diagnosed from a 24-hour record of urine output. Nocturnal polyuria, although not a urodynamic abnormality, must be considered when making a diagnosis in men with nocturia as a prominent symptom. About a third of men with LUTS have a combination of two or more underlying causes [3, 4].

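### Section 17.1.2 misreads the calibration slope: a slope of 1 is not by itself perfect agreement, and a slope below or above 1 does not mean over- or under-prediction

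*Protocol*

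**What the plan says.** Section 17.1.2 of the protocol states: "Calibration will be evaluated in two ways".

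- **Grouped comparison.** Within quintiles or deciles of predicted probability, "the average predicted probability will be compared with the corresponding observed proportions". This is supported by a visual check: "Calibration plots of average observed probability against predicted probability will be used to visually assess calibration".
- **Slope.** Calibration is to be quantified by "estimating the calibration slope of the prognostic index (linear predictor) using logistic regression with the linear predictor as the covariate".

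The section closes with the interpretation of that slope. First: "The value for the calibration slope should ideally be one signifying perfect agreement between the predicted probabilities and the observed probabilities". Then a slope below 1 "indicates that a model over-predicts while a calibration slope" above 1 "indicates under prediction". Neither calibration-in-the-large nor an observed-to-expected ratio is mentioned.

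**The concern.** A calibration slope shows whether the predictions are spread too widely or too narrowly on the log-odds scale. It carries no information about their overall level, and over- and under-prediction are questions of level. The protocol attaches the vocabulary of level to a measure of spread, and it treats one of two necessary conditions as sufficient.

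This matters because the decision aid (section 10.1) shows GPs and patients a probability for each of three diagnoses. A report that follows section 17.1.2 literally could describe those probabilities as in perfect agreement when all of them are too high, or could name the wrong direction of error. It could also contradict the grouped comparison and plot presented beside it, and the text gives no rule for reconciling the two.

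**Working it through.** The protocol gives no calibration figure to reproduce, so the check is whether the stated readings follow from the stated regression.

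**Inputs**
- Prevalences (section 4): detrusor overactivity 57%, bladder outlet obstruction 31%, detrusor underactivity 16%.
- Validation cohort (section 16.1): 325 men. The protocol's event counts reproduce: 325 × 0.16 = 52, 325 × 0.31 = 100.75 (101) and 325 × 0.57 = 185.25 (185).
- Assumption: the true linear predictor is normal with SD 1. The protocol gives no value.
- The shifts and slopes below are chosen to illustrate. They are not forecasts for this study.

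**Model.** Let LP be the model's linear predictor, with logit P(Y = 1) = a + b × LP. Agreement requires a = 0 and b = 1 together. Calibration-in-the-large is the intercept when LP is entered as an offset, that is, with b fixed at 1.

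**1. Slope 1 is not sufficient.** Multiply every predicted odds by c. The new predictor is LP + ln c, so b stays exactly 1 and a becomes −ln c. For c = 2, a = −0.693. This holds for any SD. Simulation with 300,000 men per scenario gave:

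| Diagnosis | Slope | Mean predicted | Observed | Deciles over-predicted |
|---|---|---|---|---|
| Detrusor underactivity | 0.999 | 25.8% | 16.0% | 10 of 10 |
| Bladder outlet obstruction | 0.999 | 44.5% | 30.9% | 10 of 10 |
| Detrusor overactivity | 0.993 | 70.3% | 57.0% | 10 of 10 |

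The size of the gap does depend on the SD. A man with true risk p is given 2p/(1 + p). That function is concave, so at 16% prevalence the mean prediction cannot exceed 0.32/1.16 = 27.6%, the value when the SD is 0. It falls towards 16% as the SD grows. The 25.8% at SD 1 lies inside that range.

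**2. Slope below 1 is not over-prediction.** When b < 1, predictions are too high above LP = a/(1 − b) and too low below it.
- *Mean correct, slope 0.7.* For bladder outlet obstruction the lowest decile is 3.0% predicted against 6.5% observed, and the highest 78.8% against 67.8%. Both directions occur at once.
- *Mean too low, slope 0.7.* For detrusor underactivity the mean is 8.0% predicted against 16.0% observed, and every decile is under-predicted. The fitted a = 0.251 and b = 0.694 put the crossing at 0.251/0.306 = 0.82, a predicted risk of about 69%. The top decile averages 34.4%, well below that. The protocol's reading has the wrong sign.

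**3. Slope above 1 is not under-prediction.**
- *Mean correct, slope 1.3.* For bladder outlet obstruction the lowest decile is 9.9% against 6.6%, and the highest 60.7% against 68.3%. The predictions are too narrow.
- *Mean too high, slope 1.3.* For detrusor underactivity the mean is 24.0% against 16.0%, and every decile is over-predicted. Again the sign is wrong.

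**4. What the extra measure adds at n = 325.** In 500 simulated validation sets per prevalence with predicted odds doubled, the mean slope was 1.00 to 1.01 (SD 0.14 to 0.18). Mean calibration-in-the-large was about −0.71 (SD 0.12 to 0.17), and it differed from 0 at the 5% level in every set.

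**5. The ordinary intercept is not a substitute.** With the slope left free, the intercept is not calibration-in-the-large. For detrusor underactivity at slope 0.7 with the mean correct, the free intercept was −0.42 while calibration-in-the-large was −0.01.

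**The case against.** The best defence is that the slope is only half of the calibration plan. The quintile or decile comparison sets mean predicted against observed risk numerically, and a uniform shift would put every group off in the same direction. That stands. A reader might infer that a badly shifted model would pass unseen or be declared perfect. The protocol does not support this: it is true only of the slope sentences taken alone.

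A reader might also infer that the primary outcome is biased. It is not. Sensitivity and specificity are counted against urodynamics in the validation cohort, so if a level shift moves men across a threshold, the observed accuracy already reflects it. Nor does a wrong decision follow automatically, because the protocol ties no acceptance limit or recalibration step to the slope.

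The missing intercept is weak ground on its own. Only the protocol was available, and such a statistic is often left to the SAP. Nothing in the protocol suggests that prevalence will differ between the two cohorts, so a shift of the illustrated size is not predicted here.

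Finally, section 17.1.1 links shrinkage to overfitting and to avoiding extreme predictions. That suggests the authors know what a slope below 1 detects and that the wording is loose. This may explain the error but does not remove it. The sentences are affirmative statements in the protocol, and an analyst who follows them would report the wrong thing.

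**Conclusion.** The point holds as an error of interpretation. A slope of 1 is necessary but not sufficient for agreement. Slopes below and above 1 mean predictions that are too extreme and not extreme enough, and neither gives the direction of overall error. These statements follow from the algebra of the regression and do not depend on any assumed value. The sizes do: 25.8% against 16.0% at a slope of about 1, and 8.0% against 16.0% at a slope of 0.7, both rest on a linear predictor SD of 1 and on chosen shifts.

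The consequence is confined to what is concluded and published about the calibration of the aid's probabilities. The primary accuracy estimates are unaffected, and a large level shift would probably be seen in the grouped comparison.

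**What to change.** Replace the last two sentences of section 17.1.2 with wording such as: *Good calibration requires calibration-in-the-large of 0 and a slope of 1 together. Calibration-in-the-large below 0 indicates overall over-prediction and above 0 overall under-prediction. A slope below 1 indicates predictions that are too extreme; a slope above 1 indicates predictions that are not extreme enough.*

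For each of the three models, report calibration-in-the-large (the intercept with the linear predictor as offset) beside the slope, both with 95% confidence intervals, and carry the same wording into the SAP.

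Do not add an intercept-updating step to the validation accuracy results. Accuracy re-estimated after updating on the validation cohort would no longer meet the section 5.1 objective of an independent validation cohort, so any updated model would have to be labelled as not independently validated.

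The cost is two sentences and one extra one-parameter fit per diagnosis, with no new data.

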## **17.2 Qualitative analysis**

Interviews will be audio-recorded and transcribed, and transcribed data entered into qualitative analysis software. Clinician and patient interview data will be analysed separately. Due to the expected homogeneity of data resulting from the semi-structured interviews, we will use Framework Analysis to identify key themes (codes) emerging from the data, including those relating to usability and acceptability. The matrix output will allow us to compare themes across cases (patient/clinician) and within individual cases. We will assess the point of data saturation by continual review of interview transcripts.

## **17.3 Cost effectiveness analysis**

The study will highlight all potential changes to routine care where cost savings/expenditures will occur, and therefore aid the determination of all cost parameters and health related outcomes which must be considered in any future cost-effectiveness analysis.

For the purposes of this work, a simple cost comparison will be performed with any relevant data routinely collected or made available throughout the study. Where economic data is not readily available, data will be sought from published resources, or estimated expert opinion. This will allow an early indication of the potential cost implications of the routine use of the clinical decision aid and, importantly, will inform planning for future clinical evaluations and cost-effectiveness analysis.

## **17.4 Other Analyses**

### **17.4.1 Referral rates**

The potential impact of the decision aid on referral rates will be calculated by expressing the difference between rates occurring during GP practice participation in the PriMUS study including consideration of urodynamic diagnoses provided by use of the reference test with the historical control of practices participating in the CPRD data collection.

## **18 Data Management**

### **18.1 Source data**

The source data for PriMUS study will be from a variety of sources. Data will be collected using an electronic system with paper CRF back up. There will also be data collected from participant's medical notes and patient reported questionnaires. Source data from flowmeters and urodynamic assessments will be recorded, downloaded and stored electronically in individual patient folders within the database.

Training for completion of study CRFs will be provided to the appropriate study staff prior to study commencement at site initiation.

### **18.2 Completion of CRFs**

All assessments and data collection will be completed using web-based CRFs. This is a secure encrypted system accessed by username and password, and complies with Data Protection Act standards. In the event that the web-based system is not accessible, paper CRFs will be used to record data. The data will then be inputted into the web-based system once it is accessible. A full data management plan will accompany this protocol and will be stored in the TMF.

### **18.3 Electronic CRFs**

We intend to develop data recording for this study as a web-based system. This is a secure encrypted system accessed by an institutional password, and complies with Data Protection Act standards.

A user password will be supplied to investigators upon completion of all processes required prior to opening.

### **18.4 Paper CRFs**

If the electronic database is not available, paper CRFs will be used and data will be entered on to the database at a later point. In accordance with the principles of GCP, the PI is responsible for ensuring accuracy, completeness, legibility and timeliness of the data reported to the CTR in the CRFs.

CRF pages and data received by the CTR from participating study sites will be checked for missing, illegible or unusual values (range checks) and consistency over time.

If missing or questionable data are identified, a data query will be raised on a data clarification form. The data clarification form will be sent to the relevant participating site. The site shall be requested to respond to the data query on the data clarification form. The case report form pages should not be altered. All answered data queries and corrections should be signed off and dated by a delegated member of staff at the relevant participating site. The completed data clarification form should be returned to the CTR and a copy retained at the site along with the participants' CRFs. The CTR will send reminders for any overdue data. It is the site's responsibility to submit complete and accurate data in timely manner. Further details of data management procedures can be found in the Data Management Plan.

### **18.5 Qualitative study data management**

All the information, including any personal information (e.g. patient name), will be kept completely confidential. Recordings will not be labelled with patient name. Any written report of the research will have the patient's name removed. Written quotes of what the patient says in the interview may be used word for word, but quotes will be anonymised. Patient names will not appear on any publications. All study related records will be stored for 15 years. The results are likely to be published in medical journals over the next few years. The patient will not be personally identified in any report or publication. Full details of data management will be specified in the Data Management Plan.

## **19 Protocol/GCP Non-Compliance**

The PI / local researcher should report any non-compliance to the study protocol or the conditions and principles of Good Clinical Practice to the CTR in writing as soon as they become aware of it. The CTR will assess the nature and severity of any issues of non-compliance in accordance with their SOPs.

## **20 End of Study definition**

The end of the study is defined as the date of final data capture to meet the study endpoints. Sponsor must notify REC of the end of a clinical study within 90 days of its completion or within 15 days if the study is terminated early.

## **21 Archiving**

The TMF and TSF containing essential documents will be archived at an approved external storage facility for a minimum of 15 years. The CTR will archive the TMF and TSFs on behalf of the Sponsor. The Principal Investigator is responsible for archival of the ISF at site on approval from Sponsor. Essential documents pertaining to the study shall not be destroyed without permission from the Sponsor.

## **22 Regulatory Considerations**

### **22.1 Ethical and governance approval**

This Study Protocol has been submitted to a Research Ethics Committee (REC) that is legally “recognised” by the United Kingdom Ethics Committee Authority (UKECA) for review and approval. A favourable ethical opinion will be obtained from the REC before commencement of any study procedures (including recruitment of participants).

This Study Protocol will be submitted through the relevant permission system for global governance via Health and Care Research Wales (HCRW) Permissions Coordinating Unit (PCU).

Approval will be obtained from the host care organisation who will consider local governance requirements and site feasibility. The Research Governance approval of the host care organisation must be obtained before recruitment of participants within that host care organisation.

All substantial protocol amendments must be approved by the REC responsible for the study, in addition to approval by NHS Research and Development (R&D). Minor amendments will not require prior approval by the REC.

If the study is stopped due to adverse events or an urgent safety measure it will not be recommenced without reference to the REC responsible for the study.

The outcome of the study (e.g. completed) will be reported to the REC responsible for the study within 90 calendar days of study closure. In the event of the study being prematurely terminated a report will be submitted to the REC responsible for the study within 15 calendar days.

A summary of the results will be submitted to the REC responsible for the study within one year of completion of study closure.

